3.3.1 COHORT REVIEW PROCESS

A review of safety data and other supporting data required to make a recommendation with regard to dose escalation will be conducted prior to opening any new cohort. Dose assignment for each cohort will be carried out, using all available data, by the Sponsor in conjunction with the chief investigator, and principal investigators (PIs). Cohort Review Meetings will be held to determine if the dose level has been tolerated by the subjects, to determine if it is safe to escalate the dose, and to determine the next dose level. These reviews will be triggered when sufficient subjects have completed their first cycle of treatment at a particular dose. These meetings will be led by the Sponsor and will include

as a minimum the chief investigator or his designee and a representative from each site with a subject in the cohort under discussion. The safety data, including a list of DLTs and all AEs, will be reviewed along with all other available data such as PK and/or PDn data. DLTs will be the primary consideration for the purposes of dose escalation decisions; however, should cumulative toxicity become apparent this will also be taken into consideration.

Other topics to be discussed could include, but are not limited to:

- Whether the data suggest that testing of an alternative schedule should begin and if so, what initial dose and schedule would be tested;
- Whether subjects receiving subsequent cycles of SRA737 at lower dose levels could be allowed to proceed with intra-subject dose escalation.

3.3.2 DOSE ESCALATION DECISION RULES

The dose level of SRA737 will be assigned according to the number of subjects already enrolled at the current dose level, the number of DLTs (and any other drug-related AEs) observed at the current dose level and the number of subjects enrolled who are at risk of developing a DLT. When sufficient data, as determined during the Cohort Review Meeting, are available to assess these in the rolling 6 cohorts, the subsequent SRA737 dose level will be assigned according to the following:

- If the data are available from a minimum of 3 subjects who have been treated in a cohort and no DLTs have been observed at that dose level, then dose escalation can be considered.
- If the data are available from 3 subjects who have been treated in a cohort and one DLT has been observed at that dose level, then the cohort will be expanded to up to 6 subjects.
- If two DLTs have been observed at any dose level, dose escalation will stop and this dose will be defined as the maximum administered dose for that schedule.
 - The dose will be de-escalated and the previous dose level will be expanded to up to 6 subjects. If the previous dose level already included a cohort of 6 subjects, then this could be identified as the MTD unless it is decided that an intermediate dose level would be tested.
 - An intermediate dose level between the previous and current dose level may be explored following full discussion between the Sponsor and Chief Investigator.
- The maximum administered dose could also equal the MTD in the event that dose escalation is stopped before 2 DLTs are observed at a given dose level, due to the expectation that higher dose levels would be too toxic to administer to subjects.

3.4 DEFINITION OF DOSE LIMITING TOXICITY

The DLT window is defined from the first Day -7 to Day -4 dose until the end of Cycle 1 (up to 35 days).

A DLT is defined as any highly probably or probably SRA737-related event of:

- Grade 4 neutropenia or thrombocytopenia that lasts for > 7 days despite withholding dosing and/or providing supportive care (eg, hematopoietic growth factors)

Note: In the event of a Grade 4 neutropenia or Grade 4 thrombocytopenia, a full blood count must be performed at least on Day 7 after the onset of the event to determine if a DLT has occurred. The investigator must continue to monitor the subject closely until resolution to ≤ Grade 3.

- Febrile Neutropenia
- A ≥ Grade 3 thrombocytopenia with ≥ Grade 3 bleeding
- A ≥ Grade 3 nonhematological toxicity with the following possible exceptions per Cohort Review discussion:
 - Alopecia of any grade
 - Grade 3 or 4 nausea or vomiting in subjects that have not received optimal treatment with anti-emetics
 - Grade 3 or 4 diarrhea in subjects that have not received optimal treatment with anti-diarrheal medication
 - Transient, asymptomatic Grade 3 biochemical abnormalities if agreed by the Medical Monitor and the Chief Investigator
 - Grade 3 fatigue, unless there is an increase by at least 2 grades from baseline (classed as the grade prior to first dose)
- Inability to receive 75% of planned dose in the first cycle during the DLT window due to drug-related toxicity

DLTs defined above will be considered for the purposes of dose escalation decisions; however, should cumulative toxicity become apparent this will also be taken into consideration when determining either the next dose level or the RP2D(s).

All DLTs must be reported to the sponsor or sponsor's delegate within 24 hours of site staff becoming aware of the DLT, including any change made to the grade or causality of an AE that may alter its DLT status, as this may affect dose escalation decision making.

3.5 DEFINITION OF MAXIMUM TOLERATED DOSE AND RECOMMENDED PHASE 2 DOSE AND SCHEDULE

If 2 out of up to 6 subjects at the same dose level experience a DLT, as defined above, the MTD will be determined as a lower dose level for that schedule.

The RP2D and schedule will be defined at the end of the study and will take all clinically relevant toxicity, PK and PDn data into account. The RP2D will be a dose equal to or less than the MTD for the selected schedule.

3.6 COHORT EXPANSION PHASE

Prospectively-selected genetically-defined subjects will be enrolled in 6 indication-specific expansion cohorts to establish the safety profile and preliminary efficacy of SRA737. Each expansion cohort will enroll approximately 20 subjects from the following indications: metastatic CRC, HGSOC without *CCNE1* gene amplification, HGSOC with *CCNE1* gene amplification, mCRPC, advanced NSCLC, or HNSCC/SCCA.

Screening for expansion cohorts will be initiated prior to the completion of dose escalation and determination of MTD or RP2D. If a slot is not available in the Dose Escalation Cohort, eligible prospectively-selected genetically-defined subjects will be enrolled in the Expansion Cohort at the highest dose level determined to be safe and tolerable in the Dose Escalation Phase. If a subject who meets the eligibility criteria for the expansion cohorts enrolls to a Dose Escalation Cohort, that subject will count toward the sample size of 20 for that indication-specific cohort.

The goal of the expansion cohorts is to assess SRA737 across multiple tumor types in subjects who have a range of genomic profiles of interest as described in inclusion criterion 9. The sponsor may choose to refine or select particular genomic profile requirements in each (or all) Expansion Cohort(s) based on observations of tumor response and clinical benefit in the ongoing study and/or other emerging clinical and nonclinical data. The sponsor may also choose to select for alternative genomic profiles in the event profile(s) not associated with tumor responses are overrepresented in subjects already enrolled. For example, if no responses have been seen in subjects with deleterious KRAS and TP53 mutations across tumor types, the sponsor may elect to restrict further enrollment of subjects with this particular genomic profile. Also, the sponsor may select subjects such that

sufficient numbers of genetic variants within an indication are studied (for example BRCAm and BRCAwt).

3.7 INTRA-SUBJECT DOSE ESCALATIONS

Once a higher dose level has been determined to be safe in a cohort of Dose Escalation subjects, subjects who have not experienced \geq Grade 2 SRA737-related toxicity at the dose at which they are currently being treated, in the most recent prior cycle, are able to escalate to the next higher dose level for that schedule once the sponsor approves the escalation.

Only one dose level increase can be undertaken each cycle.

This intra-subject escalation will be to a dose level already evaluated at a Cohort Review Meeting and found to be acceptable from a safety perspective. If the subject(s) then goes on to experience an event meeting the definition of DLT, this information will be taken into account for future dose escalation decisions.

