5.4 DOSE MODIFICATIONS

The schedule and/or dose may be reduced for all subjects depending on emerging safety information. Decisions regarding treatment modification for individual subjects will be based on the following assessments:

- Laboratory values and AE observations from the day of dosing, to determine if treatment can be administered or should be withheld;
- Lowest (nadir) laboratory values and worst grade AE observations since the previous dose of study drug(s), to determine if a dose reduction is recommended.

Decisions to delay or adjust the dose of SRA737 should be made conservatively, using the guidelines for the most severe AEs and the worst scenario of the recommended dose reduction(s). Once the dose has been reduced, it should not be re-escalated. If any subject requires a delay in dosing for more than 28 days, the subject should be discontinued from treatment (see Section 5.6).

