5.4.1 DOSE REDUCTIONS OR DELAYS

Guidelines for dose delays due to AEs are provided in Table 2.

Table 2. Dose Delay and Discontinuation Guidelines

Event	Recommended Action
Grade 3 neutropenia or Grade 3 thrombocytopenia	
Recommend twice weekly monitoring of blood tests if the subject is to continue dosing.
Grade 4 neutropenia or thrombocytopenia or Any non-hematologic \geq Grade 3 SRA737-related toxicity*	
Consider dose interruptionIf toxicities have not resolved to \leq Grade 1 or \leq 1 grade worse than baseline with a dose interruption, continue to delay treatment for up to 4 weeks. If no recovery after 4-week delay, discontinue treatment.
If toxicities have resolved to \leq Grade 1 or \leq 1 grade worse than baseline, treatment may be reinitiated. Consider resumption of treatment at the next lowest dose level for the schedule under investigation or at a reduced dose at an alternative, intermittent schedule.

*Exceptions may include nausea, vomiting or diarrhea lasting < 48 hours, asymptomatic biochemical abnormalities lasting < 5 days, Grade 3 fatigue (unless there was an increase in severity of > 2 grades from baseline), or other event agreed with the Sponsor or Sponsor's designee.

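### The one-cycle look-back in Protocol Section 3.7 lets a subject qualify on toxicity for a dose above the one that caused that subject's own DLT-criteria event

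*Protocol*

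**What the plan says.** Three parts of the protocol govern how one subject's dose moves after toxicity. The SAP has no rule on this.

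- **Section 3.7.** Once a higher level has been found safe in dose-escalation subjects, those without related toxicity of Grade 2 or higher at their present dose "in the most recent prior cycle, are able to escalate to the next higher dose level for that schedule once the sponsor approves the escalation". The target level must have been accepted at a Cohort Review Meeting, and a subject may move up only one level per cycle. The section's only mention of DLTs looks forward, to events after the escalation.
- **Section 5.4.** "Once the dose has been reduced, it should not be re-escalated". This is the only bar tied to a subject's own history, and a reduction is what triggers it. The same section says: "Decisions to delay or adjust the dose of SRA737 should be made conservatively, using the guidelines for the most severe AEs".
- **Section 5.4.1, Table 2.** For Grade 4 neutropenia or thrombocytopenia, or related non-hematologic toxicity of Grade 3 or higher, interruption is something to consider. After recovery, "treatment may be reinitiated. Consider resumption of treatment at the next lowest dose level for the schedule under investigation"; a reduced dose on an intermittent schedule is the other option named. Febrile neutropenia, a DLT in Section 3.4, has no row of its own.

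Section 3.4 defines a DLT as probably or highly probably related to SRA737. It prescribes neither reduction nor stopping for the affected subject. Section 5.6 lists unacceptable toxicity among the reasons for which treatment may be discontinued.

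**The concern.** In a first-in-human trial, the best evidence that a dose is too high for a given person is that person's own severe reaction to it. The Section 3.7 test forgets that evidence after one clean cycle.

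Two subjects with the same event can then fall under opposite rules. The one whose dose was reduced should not return even to the dose that caused the event. The one who resumed at that dose can meet the toxicity test for a higher one, with no protocol deviation at any step. What is at stake is the safety of individual subjects, not a statistical operating characteristic.

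**Working it through.** The plan gives no figure to reproduce. The check applies the rules in order, then does the small amount of arithmetic on timing and step size.

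**Rule trace, for a subject at dose D**

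1. *Cycle n.* An event meeting the Section 3.4 criteria occurs, for example a probably related Grade 3 non-hematologic toxicity. Table 2 asks the investigator to consider interrupting.
2. *Recovery.* Table 2 lets treatment restart. A lower dose is to be considered but D is not excluded. If treatment resumes at D, there has been no reduction and the Section 5.4 bar is not triggered.
3. *Cycle n+1 at D, with no related toxicity of Grade 2 or higher.* Section 3.7 examines this cycle only, so its toxicity test is met. If related Grade 2 toxicity persisted into this cycle, the test would be met after the next clean one.
4. *Cycle n+2.* The next level above D is open if it has been cleared and the sponsor approves.

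**Can the level above D be cleared when D produced a DLT?** Yes. Under Section 3.3.2 one DLT among 3 subjects expands the cohort to up to 6, and escalation stops at two DLTs. One DLT in 6 is 1/6 = 16.7%, within the 33% limit of the MTD endpoint in Section 3.1.1. Section 3.2 allows intra-subject escalation for all subjects once a higher level is safe, with no exclusion for personal history.

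**Table 2.** It covers three event classes: Grade 3 cytopenia, Grade 4 cytopenia, and non-hematologic Grade 3 or higher. The number with a mandatory reduction is 0.

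**Timing, continuous schedule, 28-day cycles, no delay**

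- Cycle 1 is Days 1–28 and Cycle 2 is Days 29–56, so Cycle 3 Day 1 = 2 × 28 + 1 = Day 57. This is the earliest date the look-back allows for a Cycle 1 event. It requires resumption by Day 29, a clean Cycle 2 and a higher level already cleared.
- If D is itself the level under test, the date is later. Assume the added subjects finish their first cycle no earlier than this subject's Day 28. Section 3.3 sets at least 5 weeks between cohorts, so the next level clears at about Day 28 + 35 = 63. The next cycle start after that is 3 × 28 + 1 = Day 85.

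**Size of the step**

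- The typical increment after doubling ends is 25–75% (Section 3.3), so the new dose is 1 + 0.25 = 1.25 to 1 + 0.75 = 1.75 times D.
- A step of 1 + 1.00 = 2 times applies only where the next level had already been set by doubling, or where the event came after Cycle 1. A related Grade 2 or higher toxicity in Cycle 1 ends the doubling phase.

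**The case against.** The strongest reply is that several safeguards must all fail to act.

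- **Sponsor approval** is mandatory and specific to the subject, and DLTs must reach the sponsor within 24 hours (Section 3.4). This is the most substantial safeguard. But no criterion for approval is written. The DLT window closes with Cycle 1, so a later event meeting the same toxicity criteria is not covered by that notice unless it qualifies for other expedited reporting, such as an SAE.
- **Cohort clearance** is required, but it judges the dose level across a cohort, not a subject already shown to be sensitive below it.
- **Conservative adjustment** under Section 5.4, and the fact that Table 2 names only lower resumption doses, make same-dose resumption less likely. Both are guidance.
- **Cohort review** may take up "Whether subjects receiving subsequent cycles of SRA737 at lower dose levels could be allowed to proceed with intra-subject dose escalation", but this stands under "Other topics to be discussed could include, but are not limited to", so it is optional.
- **Weekly hematology** after an escalation (Section 7.2.2) detects a repeat cytopenia only after the higher dose has been given.

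The reply stands on likelihood: the path needs an investigator who does not reduce, a clean cycle, a cleared level and a sponsor who approves. It does not show that any rule closes the path.

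A second objection concerns scope, and it stands. A reader might count every Grade 4 neutropenia or thrombocytopenia as a DLT-type event. Section 3.4 does not support that: such a cytopenia meets the criteria only if it lasts more than 7 days despite withholding or supportive care. Shorter episodes should stay under the one-cycle test and sponsor approval.

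**Conclusion.** The point holds as a gap in a stated eligibility rule: after same-dose resumption and one clean cycle, an earlier DLT-criteria event no longer counts in the Section 3.7 toxicity test. The sponsor's decision is then the only remaining check that could take that subject's earlier toxicity into account, and nothing tells the sponsor to do so. It is a cheap improvement to make.

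The conclusion rests on the wording alone, and it assumes that the investigator resumes at the same dose and that a higher level has been cleared. The documents give no rate, so no number of affected subjects is claimed.

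Three stronger readings are tempting but unsupported:

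- *The safeguards have failed, or the plan directs such escalations.* The wording permits them; it does not require them, and nothing shows that any occurred.
- *The optional choice to reduce alone decides who is escalated.* The clean cycle, cohort clearance and sponsor approval also decide.
- *Day 57 and a doubled dose are the general case.* Each holds only under the conditions shown in the working.

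**What to change.** Keep the present Section 3.7 conditions and add:

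> A subject may not escalate above a dose at which, in any cycle, that subject had a probably or highly probably SRA737-related event meeting the Section 3.4 toxicity criteria (the 75%-of-planned-dose criterion applies to Cycle 1 only), unless the event was agreed to be a Section 3.4 exception by the Cohort Review or, for transient biochemical abnormalities, by the Medical Monitor and Chief Investigator.

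The exceptions should come from Section 3.4, not from the Table 2 footnote. That footnote ends with an open category ("or other event agreed with the Sponsor"), and its fatigue threshold differs: an increase of more than 2 grades, against at least 2 in Section 3.4. Reduced doses need no new clause because Section 5.4 already covers them. Grade 4 neutropenia or thrombocytopenia of 7 days or less stays under the existing test.

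Cost: one sentence, and a few subjects who could now be escalated would stay at their current dose. Adverse event grade and causality are already recorded. For events after Cycle 1, exception decisions need to be documented. The Day 7 blood count that Section 3.4 requires after a Grade 4 cytopenia should also be kept up in later cycles, because scheduled hematology falls to Days 1 and 15 from Cycle 4 (Section 7.2.2).

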3.8 SUBJECT EVALUABILITY

3.8.1 *DLT EVALUABLE*

All subjects receiving at least 75% of planned doses of SRA737 within Cycle 1 and those subjects receiving less than these planned doses of SRA737 due to DLT will be considered evaluable for dose review decisions.

3.8.2 *REPLACEMENT OF SUBJECTS*

In the Dose Escalation Phase, if agreed by the sponsor, subjects will be replaced if they receive less than 75% of planned doses of SRA737 during the DLT period for reasons other than drug-related toxicity.

In the Cohort Expansion Phase, subjects who are not response-evaluable may be replaced in order to achieve 20 response-evaluable prospectively-selected genetically-defined subjects per indication- specific expansion cohort.

4 SUBJECT SELECTION AND ENROLLMENT

Subjects who have consented to participate in the trial must first be entered in the electronic data capture system by site staff and be allocated a subject number by the electronic data capture system. Once the investigator or designated representative has confirmed the eligibility of the subject, the site must submit a completed eligibility checklist, and receive

confirmation of eligibility for a dose escalation cohort, an indication-specific cohort expansion, or both, and confirmation of the assigned dose level from the Sponsor or Sponsor's designee before the subject may be enrolled.

4.1 NUMBER OF SUBJECTS

The study will enroll up to 170 subjects including an estimated 30–50 subjects during dose escalation and 6 expansion cohorts, each consisting of approximately 20 subjects. The final number of subjects enrolled into the trial will depend on the number of dose levels, the number of subjects who participate in both the Dose Escalation and Cohort Expansion phases, and potentially alternative dose schedules explored.

4.2 SUBJECT SELECTION CRITERIA

The subject must fulfil the eligibility criteria (listed in Sections 4.2.1 and Section 4.2.2).

4.2.1 *INCLUSION CRITERIA*

Dose Escalation Phase and Cohort Expansion Phase

1. Written (signed and dated) informed consent and capable of co-operating with treatment and follow up.
- 2a. For subjects in the Dose Escalation Phase: any locally advanced or metastatic, histologically or cytologically proven solid tumor or NHL, that is relapsed after or progressing despite conventional treatment for which no conventional therapy is considered appropriate by the investigator or is declined by the subject.
- 2b. For subjects in the Cohort Expansion Phase: locally advanced or metastatic, histologically or cytologically proven malignancy of the types specified in inclusion criterion 10, for which no other conventional therapy is considered appropriate by the investigator or has been declined by the subject.
3. Life expectancy of at least 12 weeks.
4. World Health Organization (WHO) performance status of 0–1 (Appendix 1).
5. Hematological and biochemical indices within the ranges shown below, measured within one week prior to the subject receiving their first dose of investigational medicinal product (IMP).

Laboratory Test	Lower acceptable limit
Hemoglobin (Hb)	≥ 90 g/L
Absolute neutrophil count	$\geq 1.5 \times 10^9$ /L
Platelet count	$\geq 100 \times 10^9$ /L
Bilirubin	$\leq 1.5 \times$ upper limit of normal (ULN) unless due to Gilbert's syndrome in which case up to $3 \times$ ULN is permissible
Alanine aminotransferase and/or aspartate aminotransferase and Alkaline Phosphatase	$\leq 2.5 \times$ ULN unless raised due to tumor in which case up to $5 \times$ ULN is permissible
Serum Creatinine	$\leq 1.5 \times$ ULN

6. Attained the age of 18 years at the time consent is given.
7. Subjects must have archival tumor tissue available for tumor profiling or accessible tumor and willingness to consent to a biopsy for the collection of tumor tissue. Refer to Section 7.1.1 for more details.

Cohort Expansion Phase

8. Subjects must have measurable disease (per Response Evaluation Criteria in Solid Tumors, version 1.1 [RECIST v1.1]) or, for mCRPC, evaluable disease per any of the following:
 - a. Measurable disease per RECIST v1.1;
 - b. Increasing prostate specific antigen (PSA, see PCWG – Appendix 7); or
 - c. Circulating tumor cell (CTC) count of 5 or more cells per 7.5ml of blood.
9. Subjects must have tumor tissue or ctDNA evidence that their tumor harbors a combination of mutations which are expected to confer sensitivity to Chk1 inhibition. Eligibility will be determined by the Sponsor's review of genetic abnormalities detected in genes in the following categories, as listed in Appendix 6:
 - a. Key tumor suppressor genes regulating G1 cell cycle progression/arrest such as *RB1*, *TP53*, etc. For patients with NHSCC or SCCA, positive HPV status is also considered for eligibility.
 - b. The DDR pathway including *ATM*, *BRCA1*, and *BRCA2*. For patients with CRC, MMR genetic alterations and/or high microsatellite instability are also considered for eligibility.
 - c. Genetic indicators of replicative stress such as gain of function/amplification of *Chk1* or *ATR* or other related gene.
 - d. Oncogenic drivers such as *MYC*, *KRAS*, etc.
 - e. *CCNE1* gene amplification (or alternative genetic alteration with similar functional effect) is required for the *CCNE1* gene amplification-specific HGSOC cohort.
10. Subjects must meet one of the following criteria (a-e):

- a. **Metastatic CRC, defined by the following:**
 - Histologically and/or cytologically confirmed CRC, and
 - Must have received at least 1 prior regimen for advanced/metastatic disease
- b. **HGSOC, defined by the following:**
 - Histologically confirmed high-grade serous ovarian, fallopian tube or primary peritoneal cancer, and
 - Recurrent platinum-intolerant subjects, or those with platinum-resistant disease, defined as radiological evidence of disease progression within 6 months of the last receipt of platinum-based chemotherapy. Patients with platinum refractory disease (ESMO – Appendix 7) are not eligible
- c. **Advanced NSCLC, defined by the following:**
 - Locally advanced and recurrent or metastatic, histologically confirmed NSCLC, and
 - Must have received at least 1 prior regimen for advanced/metastatic disease
- d. **mCRPC, defined by the following:**
 - Histologically or cytologically confirmed adenocarcinoma of the prostate that has progressed after androgen deprivation therapy
- e. **HNSCC or SCCA, defined by the following:**
 - Histologically confirmed HNSCC from any primary site, or SCCA:
 - For HNSCC: locally advanced disease (ie, persistent or progressive disease following curative-intent radiation, and not a candidate for surgical salvage due to incurability or morbidity), or metastatic disease
 - For SCCA: locally advanced disease or metastatic disease for which no curative intent therapy is available
 - Must have received at least 1 prior regimen for advanced/metastatic disease

